15.1.1. ALL TEAES

Incidence of TEAEs will be presented by System Organ Class (SOC) and Preferred Term (PT) and also broken down further by maximum severity and relationship to study medication. Multiple occurrences for the same subject of an AE classified with the same SOC/PT will be counted only once in the summaries.

15.1.1.1. Severity

Severity is classed as mild/ moderate/ severe (increasing severity). TEAEs starting after the first dose of study medication with a missing severity will be classified as severe. If a subject reports a TEAE more than once within that SOC/ PT, the AE with the worst case severity will be used in the corresponding severity summaries.

Document:	x:\biostatistics\documentation\sap\pya18238_izana_izn-101	_sap_v1_0_2019050.docx	
Author:		Version Number:	1.0
		Version Date:	07May2019
Template No.:	CS_TP_BS016 Revision 5	Reference: CS_WI	_BS00

Effective Date: 01Apr2018

Izana Bioscience Limited PROTOCOL IZN-101

Statistical Analysis Plan

15.1.1.2. Relationship to Study Medication

Relationship, as indicated by the Investigator, is classed as "unrelated", "unlikely to be related", "possibly related", "probably related" (increasing severity of relationship). TEAEs with a missing relationship to study medication will be regarded as "probably related" to study medication. If a subject reports the same AE more than once within that SOC/ PT, the AE with the worst case relationship to study medication will be used in the corresponding relationship summaries. In addition to the summary of the four categories, a summary presenting the two categories "possibly related" and "probably related" grouped as "related" and the other two as "not related" to study medication will be produced.

15.1.2. TEAEs Leading to Discontinuation of Study Medication

TEAEs leading to permanent discontinuation of study medication will be identified by using the action taken with study medication classed as "drug withdrawal" and listed.

15.1.3. SERIOUS ADVERSE EVENTS

Serious adverse events (SAEs) are those events recorded as "Serious" on the Adverse Events page of the eCRF. A summary of serious TEAEs by SOC and PT will be prepared. A listing with the additional information collected in the eCRF for SAE will be prepared.

15.1.4. Adverse Events Leading to Death

TEAEs leading to Death are those events which are recorded as "Fatal" on the Adverse Events page of the eCRF. A listing of Adverse Events leading to death will be prepared.

15.1.5. Adverse Events of Special Interest

The following TEAEs of special interest (for which there is a specific tick box in the eCRF) will be summarized separately (but included in all other summaries):

- Pulmonary alveolar proteinosis (PAP)
- o Neutropaenia
- Myeloid suppression

 Document:
 x:\biostatistics\documentation\sap\pya18238_izana_izn-101_sap_v1_0_2019050.docx

 Author:
 Version Number:
 1.0

 Version Date:
 07May2019

Template No.: CS_TP_BS016 Revision 5

Effective Date: 01Apr2018

Copyright © 2009, 2010, 2012, 2016, 2018 IQVIA. All rights reserved. The contents of this document are confidential and proprietary to IQVIA Holdings Inc. and its subsidiaries. Unauthorized use, disclosure or reproduction is strictly prohibited.

Reference: CS_WI_BS00

15.2. DEATHS

If any subjects die during the study the information will be presented in a data listing. A subject is considered died if the outcome of an AE or of a SAE is death or if the Reason for study discontinuation is death.

15.3. LABORATORY EVALUATIONS

Results from the local laboratory will be included in the reporting of this study for Haematology, Blood Chemistry, Serum Lipids, Urinalysis (Microscopic Examination will only be listed as performed on subset of subjects where blood or protein is abnormal), Immunogenicity and Other Screening Tests.

A list of laboratory parameters to be included in the outputs is included in Appendix 3 of the protocol.

Presentations will use SI Units.

Quantitative laboratory measurements reported as "< X", i.e. below the lower limit of quantification (BLQ), or "> X", i.e. above the upper limit of quantification (ULQ), will be converted to X for the purpose of quantitative summaries, but will be presented as recorded, i.e. as "< X" or "> X" in the listings.

The following summaries will be provided for laboratory data:

- Actual and change from baseline by visit (for quantitative measurements)
- Incidence of abnormal values according to normal range criteria
- Shift from baseline according to normal range criteria (for quantitative measurements and categorical measurements)

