4.3 Justification for Dose

The namilumab drug product is a single-dose liquid solution for sc injection containing 20 mg/mL, 50 mg/mL, 80 mg/mL or 150 mg/mL namilumab active ingredient. From the NEXUS study performed in subjects with moderate-to-severe RA, it was concluded that 150 mg was the most effective dose of namilumab in subjects with RA, as well as being associated with a manageable safety profile. In addition, the chronic toxicology study in cynomolgus monkeys demonstrated that the 150 mg dose in humans lies within a favourable therapeutic window of equivalent doses in monkeys (see Section 1.1.5 in the Investigator's Brochure). Therefore, the dose of 150 mg/mL was chosen for the current study in subjects with axSpA.

Treatment-related treatment-emergent AEs (TEAEs) associated with namilumab 150 mg were single cases of infection, oropharyngeal pain/dental caries, headache, decreases in neutrophil counts/neutropenia, elevated liver function tests and decreased forced expiratory volume (FEV)/force vital capacity (FVC) (see Table 6.b in the Investigator's Brochure). Based on haematology and clinical chemistry variables, there were no clinically significant or serious cases of neutropenia or abnormal liver function and there were no cases of confirmed PAP. No deaths or treatment-related SAEs were reported in subjects receiving namilumab 150 mg. These results suggest that the 150 mg dose chosen for the current study is safe and well tolerated.

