7.0 DISCONTINUATION OF STUDY TREATMENT AND SUBJECT DISCONTINUATION/WITHDRAWAL

7.1 Discontinuation of Study Treatment

Subjects may be discontinued from study treatment for the following reasons:

- 1. Pre-treatment event or treatment-emergent AE. The subject has experienced a pre-treatment event or a treatment-emergent AE that requires early termination because continued participation imposes an unacceptable risk to the subject's health or the subject is unwilling to continue because of the pre-treatment event or AE.
 - Liver Function Test Abnormalities
 - Study medication must be discontinued immediately with appropriate clinical follow-up (including repeat laboratory tests) until the subject's laboratory profile has returned to normal/baseline status, if the following circumstances occur at any time during study medication treatment:
 - ALT or AST $> 8 \times$ ULN, or
 - ALT or AST $>5 \times$ ULN and persists for more than 2 weeks, or
 - ALT or AST >3 × ULN in conjunction with elevated total bilirubin >2 × ULN or international normalised ratio (INR) >1.5, without any anti-coagulant treatment, or
 - ALT or AST >3 × ULN with appearance of fatigue, nausea, vomiting, right upper quadrant pain or tenderness, fever, rash and/or eosinophilia (>5%).
- 2. If a diagnosis of PAP is confirmed during the course of this study (see Section 8.2.4), the subject should be withdrawn and treatment initiated as applicable.
- 3. Major protocol deviation. The discovery post-randomisation that the subject failed to meet protocol entry criteria or did not adhere to protocol requirements, and continued participation poses an unacceptable risk to the subject's health.
- 4. Lost to follow-up. The subject did not return to the clinic and attempts to contact the subject were unsuccessful. Attempts to contact the subject must be documented.
- 5. Pregnancy. The subject is found to be pregnant.

Subjects who discontinue study treatment will not be replaced.

See the SoA for data to be collected at the time of treatment discontinuation and follow-up and for any further evaluations that need to be completed.

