9.4.2 Safety Analyses

All safety analyses will be performed on the Safety Analysis Set.

TEAEs are defined as AEs that first occurred or worsened in severity after the first administration of study treatment and prior to 125 days after the last administration of study treatment.

AEs will be coded using the Medical Dictionary for Regulatory Activities (MedDRA). For each study treatment, numbers of TEAEs and incidence rates will be tabulated by preferred term and system organ class.

TEAEs by maximum severity, TEAEs by relationship to study treatment, SAEs, TEAEs leading to death and TEAEs leading to discontinuation of study treatment will be tabulated for each treatment group. Commonly occurring TEAEs, i.e., those that occur in 5% or more of the subjects in either treatment group, will be summarised using descriptive statistics.

All laboratory test results, vital signs measurements, ECG results, weight and body mass index (BMI) will be summarised for each treatment group using descriptive statistics at each scheduled visit for raw numbers and change from baseline. The incidence of treatment-emergent abnormal laboratory, vital sign and ECG values will also be summarised using descriptive statistics.

visit for raw numbers and change from baseline. The incidence of treatment-emergent abnormal laboratory, vital sign and ECG values will also be summarised using descriptive statistics.

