6.3. RETESTS, UNSCHEDULED VISITS AND EARLY TERMINATION DATA

In general, for by-visit summaries, data recorded at the nominal visit will be presented. Unscheduled measurements will not be included in by visit summaries but will contribute to the

Document:	x:\biostatistics\documentation\sap\pya18238_izana_ izn-101	_sap_v1_0_2019050.docx	
Author:		Version Number:	1.0
		Version Date:	07May2019
Template No.:	CS_TP_BS016 Revision 5	Reference: CS_WI	_BS00

Effective Date: 01Apr2018

best/ worst case value where required (e.g. shift table).

In the case of a retest (same visit number assigned), the earliest available measurement for that visit will be used for by-visit summaries.

Early termination data will be mapped to the next available visit number for by-visit summaries. Listings will include scheduled, unscheduled, retest and early discontinuation data.

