15.3.1. LABORATORY REFERENCE RANGES AND ABNORMAL CRITERIA

Quantitative laboratory measurements will be compared with the relevant laboratory reference ranges in SI units and categorized as:

- Low: Below the lower limit of the laboratory reference range.
- Normal: Within the laboratory reference range (upper and lower limit included).

Document:	x:\biostatistics\documentation\sap\pya18238_izana_ izn-101	_sap_v1_0_2019050.docx	
Author:		Version Number:	1.0
		Version Date:	07May2019
Template No.	CS_TP_BS016 Revision 5	Reference: CS W	BS00

Effective Date: 01Apr2018

High: Above the upper limit of the laboratory reference range. •

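### SAP 15.3 drops the treatment-emergent condition that protocol 9.4.2 sets for laboratory abnormalities, SAP 15.5 omits the vital-sign counterpart, and no planned laboratory summary shows how far a value is out of range

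*SAP*

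**What the plan says.** Protocol 9.4.2 states: "The incidence of treatment-emergent abnormal laboratory, vital sign and ECG values will also be summarised using descriptive statistics".

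SAP 15.3 lists three laboratory summaries:
- actual values and change from baseline by visit;
- "Incidence of abnormal values according to normal range criteria";
- a shift table by the same normal-range criteria.

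SAP 15.3.1 sets the criteria: "Quantitative laboratory measurements will be compared with the relevant laboratory reference ranges in SI units and categorized as" Low, Normal or High. It has no grades and no multiples of ULN.

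SAP 15.5 plans only changes for vital signs (from baseline, and from before to after dosing). SAP 15.4 gives ECGs a shift table on the investigator's normal/abnormal judgement. SAP 3.3 lists five changes from the protocol: the full analysis set, the per-protocol set, the interim analysis, the ASAS20 definition and the removal of ASAS70. None concerns safety summaries.

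Protocol 4.3 names, among the treatment-related events seen at 150 mg, "decreases in neutrophil counts/neutropenia, elevated liver function tests". Protocol 8.3.6 makes neutropaenia an adverse event of special interest, and SAP 15.1.5 takes it from an eCRF tick box.

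**The concern.** Without a treatment-emergent condition, the incidence table can count abnormalities that were present before the first dose. Subjects with such abnormalities are eligible. Exclusion criterion 9 removes raised transaminases only when bilirubin is raised as well, so a subject with raised ALT or AST alone may be randomised. The same criterion excludes a neutrophil count (ANC) only below 1,000/µL, so a subject between that figure and the local lower limit may also enter.

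The second issue is degree. Liver tests and neutrophils are the laboratory parameters already linked to this dose. A reader of the study report will want to know how many subjects per arm had a marked change, and three classes cannot show that. Vital signs lose their abnormality summary altogether, with no record that this was intended.

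**Working it through.** The point concerns definitions and table content. The documents give no figure to reproduce, so the check sets the texts side by side and runs four illustrative subjects through the planned rules.

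**Protocol against SAP**

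| Data | Protocol 9.4.2 | SAP section 15 | Declared in SAP 3.3? |
|---|---|---|---|
| Laboratory | Incidence of treatment-emergent abnormal values | Incidence of abnormal values by normal range, no baseline or timing condition; plus shift table | No |
| Vital signs | Same | Changes only; no abnormality criteria or summary | No |
| ECG | Same | Shift table by investigator's judgement; no named incidence table | No |

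For ECGs the shift table gives the new abnormalities directly, so little is lost. For vital signs nothing takes the place of the promised summary.

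**Four illustrative ALT profiles** (multiples of local ULN, bilirubin in range throughout, so exclusion 9 does not remove A or B on liver tests)

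| Subject | Baseline | Worst post-baseline | SAP incidence | SAP shift | New or worse on treatment? | Above 8 × ULN? |
|---|---|---|---|---|---|---|
| A | 1.1 | 1.1 | High | High to High | No | No |
| B | 1.1 | 8.1 | High | High to High | Yes | Yes |
| C | in range | 1.1 | High | Normal to High | Yes | No |
| D | in range | 8.1 | High | Normal to High | Yes | Yes |

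- The SAP incidence counts 4 of 4. A treatment-emergent count that includes worsening gives 3 of 4 (B, C, D).
- The shift table separates A and B from C and D. It cannot separate A from B, or C from D.
- 2 of 4 exceed 8 × ULN. Neither the incidence table nor the shift table shows this.
- A rule that counted only subjects in range or missing at baseline would give 2 of 4 (C, D) and miss B. The definition therefore has to include worsening.

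**Where the reporting cut-points come from.** Protocol 7.1 already uses ALT or AST above 8 × ULN, above 5 × ULN for more than 2 weeks, "ALT or AST >3 × ULN in conjunction with elevated total bilirubin >2 × ULN or international normalised ratio (INR) >1.5", and above 3 × ULN with listed symptoms or eosinophilia. No summary in SAP section 15 refers to them.

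**What the by-visit statistics can show.** In the Schedule of Activities, Weeks 2, 10 and 28 are CRP and ESR only, so full post-baseline panels are scheduled at Weeks 6 and 12. SAP 6.3 keeps unscheduled measurements out of by-visit summaries, yet protocol 7.1 calls for repeat tests after a liver signal. A peak found between visits would therefore not appear in the by-visit minimum and maximum.

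**The case against.** The strongest reply is that most of this information is already planned. The shift table carries baseline status, and SAP 6.3 lets unscheduled values feed its worst case. Minimum and maximum are default statistics (SAP 7.1). Possible Hy's Law cases must be reported as SAEs (protocol Appendix 3) and so reach the serious TEAE table. TEAEs leading to discontinuation are listed and fall under the overall summary of subject counts in SAP 15.1. Neutropaenia has its own summary. With 42 subjects, the listings are short enough to read. Table layouts sit in a separate template (SAP 8) that is not among the documents.

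Much of that stands, and it rules out several stronger readings that a reader might infer:

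- *Treatment-emergent information is lost altogether.* It is not: the shift table keeps normal-to-abnormal moves.
- *Marked liver or neutrophil values will appear in no table.* This cannot be shown. The template is unseen, and extremes can surface in the minimum and maximum or as SAEs.
- *The SAP breaks a promise to tabulate the stopping limits.* The protocol made no such promise. The absence is a reporting gap, whereas the missing treatment-emergent condition is a departure.
- *ANC 1,000/µL is an on-treatment limit.* It is an entry criterion only; the protocol gives no on-treatment ANC limit.
- *The 6:1 allocation makes the problem larger.* One subject in 6 weighs more than one in 36 in every binary safety count, with or without the fix.
- *Pooling over local laboratories confounds laboratory with arm.* The documents do not say how subjects are spread over centres. Change from baseline and classification by the relevant laboratory's own range address much of the difference.

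What the reply does not answer is the count by degree. Minimum and maximum give one value per arm and visit, not a number of subjects, and are not scaled to the local ULN. An isolated value above 8 × ULN need not be an SAE. The tick box records a judgement, not the ANC.

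**Conclusion.** The point holds as an undeclared departure in two places, the laboratory incidence table and the vital-sign abnormality summary, together with a gap in showing the degree of laboratory change. It concerns descriptive safety tables only: SAP section 15 plans no statistical comparison between arms for safety, and the efficacy analyses are unaffected. It is worth correcting because liver tests and neutrophils are the laboratory parameters this protocol itself singles out.

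Two assumptions apply. SAP 15.3 does not say whether baseline values or subjects abnormal at entry count towards the incidence; the conclusion is that nothing in the text excludes them, not that they will certainly be counted. The remark that a subject can enter with an ANC below range assumes a local lower limit above 1,000/µL, because the documents give no reference ranges. The number of subjects affected cannot be estimated from the documents.

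**What to change.** 1. In SAP 15.3, define a treatment-emergent laboratory abnormality as a post-baseline value outside the local range that was in range or missing at baseline, or that has worsened from an abnormal baseline. State how worsening is judged, and base the incidence table on this definition.
2. In SAP 15.5, restore the vital-sign abnormality summary with stated criteria, or record its removal in SAP 3.3.
3. Add one descriptive table by arm, including unscheduled values. Count subjects whose worst post-baseline ALT or AST exceeds 3, 5 and 8 × local ULN, and those with ALT or AST above 3 × ULN together with bilirubin above 2 × ULN. State whether the combined criterion needs both values from the same sample. These are the figures already in protocol 7.1, used here only for reporting. The persistence, INR and symptom parts of 7.1 can stay in listings.
4. Add a summary of the lowest post-baseline ANC per subject. If 1,000/µL is shown, label it as the protocol's entry limit.

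The cost is one or two extra safety tables and a short SAP amendment, using data already collected. It should be settled before the final unblinding.

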15.3.1. LABORATORY REFERENCE RANGES AND ABNORMAL CRITERIA

Quantitative laboratory measurements will be compared with the relevant laboratory reference ranges in SI units and categorized as:

- Low: Below the lower limit of the laboratory reference range.
- Normal: Within the laboratory reference range (upper and lower limit included).

Document:	x:\biostatistics\documentation\sap\pya18238_izana_ izn-101	_sap_v1_0_2019050.docx	
Author:		Version Number:	1.0
		Version Date:	07May2019
Template No.	CS_TP_BS016 Revision 5	Reference: CS W	BS00

Effective Date: 01Apr2018

High: Above the upper limit of the laboratory reference range. •

15.4. ECG EVALUATIONS

The following ECG parameters (as collected in the eCRF) will be summarized:

- HR (bpm) •
- PR Interval (msec) •
- QRS Interval (msec) •
- QT Interval (msec) •
- QTc Interval (msec) •
- Overall assessment of ECG (Investigator's judgement):
 - o Normal
 - Abnormal, Not Clinically Significant
 - o Abnormal, Clinically Significant

The following summaries will be provided for ECG data:

- Actual and change from baseline by visit (for quantitative measurements)
- Shift from baseline according to Investigator's judgement •

15.5. VITAL SIGNS

The following Vital Signs measurements will be reported for this study:

- Systolic Blood Pressure (mmHg)
- Diastolic Blood Pressure (mmHg) •
- Pulse Rate (bpm) •
- Temperature (^{0}C) •
- Weight (Kg) •

The following summaries will be provided for Vital Signs data:

Actual change from baseline and change from pre-dose to post-dose by visit

Document:	x:\biostatistics\documentation\sap\pya18238_izana_izn-101	_sap_v1_0_2019050.docx	
Author:		Version Number:	1.0
		Version Date:	07May2019
Template No.	CS_TP_BS016 Revision 5	Reference: CS_W	_BS00

Template No.: CS_TP_BS016 Revision 5

Effective Date: 01Apr2018

15.6. Physical Examination

Physical examination results will only be listed.

15.7. OTHER SAFETY ASSESSMENTS

15.7.1. PULMONARY ALVEOLAR PROTEINOSIS

15.7.1.1. Medical Research Council (MRC) Breathlessness Scale

Shift from baseline in MRC scale (collected in the eCRF) will be summarized as a qualitative variable.

15.7.1.2. Chest X-ray

Chest X-ray results (normal, abnormal) will be provided by local (Screening) or central reader and only be listed.

15.7.1.3. Lung Function Testing

The actual value and the change from baseline to each time point will be summarized for forced expiratory volume in the first second (FEV₁), forced vital capacity (expiratory) (FVC) and peak expiratory flow rate (PEF) (collected in the eCRF).

15.7.1.4. Pulse Oximetry

The change from baseline in saturation of peripheral oxygen (SpO₂) (collected in the eCRF) will be summarized.

15.7.1. SAFETY PARAMETERS THAT WILL ONLY BE LISTED

Details of SAE Details of Adverse events of special interests IP overdose report Pregnancy reports Genetic results (HLA-B27)

 Document:
 x:\biostatistics\documentation\sap\pya18238_izana_izn-101_sap_v1_0_2019050.docx

 Author:
 Version Number:
 1.0

 Version Date:
 07May2019

Template No.: CS_TP_BS016 Revision 5

Effective Date: 01Apr2018

Copyright © 2009, 2010, 2012, 2016, 2018 IQVIA. All rights reserved. The contents of this document are confidential and proprietary to IQVIA Holdings Inc. and its subsidiaries. Unauthorized use, disclosure or reproduction is strictly prohibited.

Reference: CS WI BS00

Page 32 of 36

16. DATA NOT SUMMARIZED OR PRESENTED

The other variables and/or domains not summarized or presented are:

• Comments

These domains and/or variables will not be summarized or presented but will be available in the clinical study database.

Document: x:\biostatistics\documentation\sap\pya18238_izana_izn-101_sap_v1_0_2019050.docx

Author:

Version Number: 1.0 Version Date: 07May2019 Reference: CS_WI_BS00

Template No.: CS_TP_BS016 Revision 5

Effective Date: 01Apr2018

17. **PARTIAL DATE CONVENTIONS**

Imputed dates will NOT be presented in the listings.

ALGORITHM FOR TREATMENT EMERGENCE OF ADVERSE EVENTS:

START DATE	STOP DATE	ACTION
Known	Known	If start date < study med start date, then not TEAE If start date >= study med start date up to 125 after study med stop date, then TEAE
	Partial	If start date < study med start date, then not TEAE If start date >= study med start date up to 125 after study med stop date, then TEAE
	Missing	If start date < study med start date, then not TEAE If start date >= study med start date up to 125 after study med stop date, then TEAE
Partial, but known components show that it cannot be on or after study med start date	Known	Not TEAE
	Partial	Not TEAE
	Missing	Not TEAE
Partial, could be on or after study med start date	Known	If stop date < study med start date, then not TEAE If stop date >= study med start date up to 125 after study med stop date, then TEAE
	Partial	Impute stop date as latest possible date (i.e. last day

Document: x:\biostatistics\documentation\sap\pya18238_izana_izn-101_sap_v1_0_2019050.docx

Author:

Version Number: Version Date: 07May2019 Reference: CS_WI_BS00

1.0

Template No.: CS_TP_BS016 Revision 5

Effective Date: 01Apr2018

Page 34 of 36

	-	
START DATE	STOP	ACTION
	DATE	
		of month if day unknown or 31st December if day
		and month are unknown), then:
		If stop date < study med start date, then not TEAE
		If stop date >= study med start date, then TEAE
	Missing	Assumed TEAE
Missing	Known	If stop date < study med start date, then not TEAE
Missing	Known	If stop date < study med start date, then not TEAE If stop date >= study med start date, then TEAE
Missing	Known Partial	If stop date < study med start date, then not TEAE If stop date >= study med start date, then TEAE Impute stop date as latest possible date (i.e. last day
Missing	Known Partial	If stop date < study med start date, then not TEAE If stop date >= study med start date, then TEAE Impute stop date as latest possible date (i.e. last day of month if day unknown or 31st December if day and month are unknown), then:
Missing	Known Partial	If stop date < study med start date, then not TEAE If stop date >= study med start date, then TEAE Impute stop date as latest possible date (i.e. last day of month if day unknown or 31st December if day and month are unknown), then: If stop date < study med start date, then not TEAE
Missing	Known Partial	If stop date < study med start date, then not TEAE If stop date >= study med start date, then TEAE Impute stop date as latest possible date (i.e. last day of month if day unknown or 31st December if day and month are unknown), then: If stop date < study med start date, then not TEAE If stop date >= study med start date, then TEAE

ALGORITHM FOR PRIOR / CONCOMITANT MEDICATIONS:

START DATE	STOP DATE	ACTION
Known	Known	If stop date < study med start date, assign as prior If stop date >= study med start date and start date <= end of treatment, assign as concomitant If stop date >= study med start date and start date > end of treatment, assign as post study

Document:	x:\biostatistics\documentation\sap\pya18238_izana_ izn-101_sap_v1_0_2019050.docx		
Author:		Version Number:	1.0
		Version Date:	07May2019
Template No.	CS_TP_BS016 Revision 5	Reference: CS_WI	_BS00

Effective Date: 01Apr2018

Page 35 of 36

START DATE	STOP DATE	ACTION
	Partial	Impute stop date as latest possible date (i.e. last day of month if day unknown or 31st December if day and month are unknown), then: If stop date < study med start date, assign as prior If stop date >= study med start date and start date <= end of treatment +14 days, assign as concomitant If stop date >= study med start date and start date > end of treatment + 14 days, assign as post treatment
	Missing	If stop date is missing could never be assumed a prior medication If start date <= end of treatment, assign as concomitant If start date > end of treatment, assign as post treatment
Partial	Known	Impute start date as earliest possible date (i.e. first day of month if day unknown or 1st January if day and month are unknown), then: If stop date < study med start date, assign as prior If stop date >= study med start date and start date <= end of treatment + 14 days, assign as concomitant If stop date >= study med start date and start date > end of treatment + 14 days, assign as post treatment

Document: x:\biostatistics\documentation\sap\pya18238_izana_izn-101_sap_v1_0_2019050.docx

Author:

Version Number: 1.0 Version Date: 07May2019 Reference: CS_WI_BS00

Template No.: CS_TP_BS016 Revision 5

Effective Date: 01Apr2018

Page 36 of 36

START DATE	STOP DATE	ACTION
	Partial	Impute start date as earliest possible date (i.e. first day of month if day unknown or 1st January if day and month are unknown) and impute stop date as latest possible date (i.e. last day of month if day unknown or 31st December if day and month are unknown), then: If stop date < study med start date, assign as prior If stop date >= study med start date and start date <= end of treatment + 14 days, assign as concomitant If stop date >= study med start date and start date > end of treatment + 14 days, assign as post treatment
	Missing	Impute start date as earliest possible date (i.e. first day of month if day unknown or 1st January if day and month are unknown), then: If stop date is missing could never be assumed a prior medication If start date <= end of treatment +14 days, assign as concomitant If start date > end of treatment + 14 days, assign as post treatment
Missing	Known	If stop date < study med start date, assign as prior If stop date >= study med start date, assign as concomitant Cannot be assigned as 'post treatment'
	Partial	Impute stop date as latest possible date (i.e. last day of month if day unknown or 31st December if day and month are unknown), then: If stop date < study med start date, assign as prior If stop date >= study med start date, assign as concomitant Cannot be assigned as 'post treatment'
	Missing	Assign as concomitant

 Document:
 x:\biostatistics\documentation\sap\pya18238_izana_izn-101_sap_v1_0_2019050.docx

 Author:
 Version Number:
 1.0

 Version Date:
 07May2019

 Template No.:
 CS_TP_BS016 Revision 5
 Reference:
 CS_WI_BS00

Effective Date: 01Apr2018

Statistical Analysis Plan - v1.0 - SAP - 29-May-2019

Electronic Signature Manifestation

